10.1 Safety Planning & Connection and Support Planning

Both intervention arms include safety planning or connection and support planning. **Safety Planning is defined according to recommendations for usual care from the Joint Commission and the Suicide Prevention Resource Center's Evidence-Based Practices, and includes screening, clinical management, safety planning as described by Stanley and Brown,⁵⁵ careful discharge planning, and referral to outpatient**

mental health services.^{7-9,14} Safety planning is designed to be completed collaboratively with patients at risk for suicide and is comprised of an individually tailored plan of actions to take if suicidal ideation or a crisis recur.^{21,55,56} Specifically, safety planning is a therapeutic clinical intervention that begins with a suicide narrative and includes each of the following six elements:

1. Identifying potential warning signs of suicidal crisis,
2. Utilizing internal coping strategies,
3. Engaging social contacts and settings that provide distraction,
4. Engaging family and friends for social support to resolve the crisis,
5. Reaching out to mental health professionals including suicide prevention hotlines, and
6. Restricting access to lethal means.^{55,56}

A full safety plan is clinically indicated for any patient with a moderate to high risk for suicide (generally, a C-SSRS score of 3-6, plus clinical judgement of their provider), or any patient whose current visit is related to a suicide attempt. Collaborative safety planning is distinct from “No Suicide Contracts,” which elaborate what patients will *not* do, are not individually-tailored, are not evidence-based, and may actually be iatrogenic.⁵⁷

A connection and support plan will be completed in lieu of a safety plan for patients with low levels of suicide risk (generally a C-SSRS score of 1-2 and/or clinical judgement of their provider). The connection and support plan will include psychoeducation on suicide prevention; a discussion of social support; sharing of crisis resources (including the Hotline) and contact information for professional resources such as therapists, as well as a discussion of when to engage those resources; lethal means counselling focused on firearms safety and medication safety generally; and reasons for living.

10.2 Safety Planning Intervention Plus Phone-Based Follow-Up (SPI+)

The Safety Planning Intervention (SPI+)¹⁻⁷ includes safety planning plus a structured telephone-based intervention following discharge from the emergency department or departure from a primary care clinic. For the SPARC Trial, Hotline follow-up specialists will call participants within 72 hours of study enrollment to (1) conduct a brief suicide risk assessment; (2) review and revise the participant’s connection and support plan or safety plan; and (3) provide support with treatment engagement, if indicated. Participants will receive at least one and optional additional phone calls as part of the SPI+ follow-up intervention generally delivered according to the following schedule: days 3, 7, 14, 30, 60, 90.^{8,9} Modifications may be made to the schedule due to weekends, holidays, or participant availability, and additional calls may be scheduled as desired by the participant. The follow-up will stop once the participant is successfully engaged in outpatient treatment or does not desire further follow-up support. In instances where participants cannot be reached for an initial phone call within 72 hours, Hotline staff will continue to attempt to schedule and complete the phone call. A minimum of three attempts to schedule and complete each phone call will be made.

This version of the intervention differs from the Stanley/Brown SPI+ model in that the structured follow-up

will be conducted by Hotline follow-up specialists, rather than by specially trained social workers or psychologists. In this pragmatic clinical trial, we are committed to testing a model that could be feasibly scaled up and replicated in other rural and resource-limited settings. The schedule was adopted from similar military follow-up programs: the Marine Intercept Program⁹ and the Navy Sailor Assistance and Intercept for Life (SAIL) Program.⁸ We selected this schedule given that we wanted to offer a longer follow-up window than the traditional SPI+ in order to support treatment engagement because connecting with outpatient behavioral health treatment (such as a counselor or therapist) typically takes 4-6 weeks for patients at low risk for suicide in our health system.

10.4 Safety Planning Intervention + (SP+CC)

SP+CC will include safety planning, plus caring contacts from the Hotline. Suicide prevention hotlines have been shown to be an effective means of mitigating active suicide risk.^{58,59} **SP+CC follow-up will consist of one phone conversation, whenever possible within the first 72 hours following study enrollment,** to connect and establish rapport between the follow-up specialist and participant. In instances where participants cannot be reached within 72 hours, Hotline staff will make at least three attempts. If the phone call cannot be successfully completed after at least three attempts, the caring contacts will be started without the phone call.

The call will be followed by a series of 25 personalized caring contacts sent over the course of 12 months via text message or email.⁶⁰ The frequency and cadence of caring text or email messages will be consistent for all participants according to a schedule that was developed in consultation with PLES Advisors to ensure it is culturally and age appropriate. Caring text or email messages will be sent according to the following schedule: three in the first week, 6 weekly, 6 bi-weekly, 4 monthly; two bi-monthly, and one each for the participant's birthday, Thanksgiving, Christmas, and New Year's (total of 25 over 12 months).⁶⁰ The exact schedule and content of the messages may vary slightly to account for weekends and holidays (messages will generally be sent M-F during working hours). While there is no expectation that participants respond to the text messages, some participants may choose to respond. Hotline Follow-Up Specialists will review incoming text messages and phone calls from study participants and will respond according to the Hotline's internal operating procedures. These additional contacts will take place outside of the structured study protocol and will not be under the purview of SLHS institutional policies. The number of individual responses, content, and timing of text or email messages will be tracked and shared with the study team. Response and ongoing contacts as part of the Hotline's processes will not alter the timing or frequency of caring contacts established by the study protocol.

10.5 Definition of Minimal Intervention

To be considered a recipient of the study interventions, participants must have completed a connection and support plan or a safety plan at St. Luke's. If randomized to the SPI+ comparator, participants must receive at least one phone call from the Hotline. If randomized to the SP+CC comparator, participants

must be sent at least 4 caring text or email messages.

10.6 Process Evaluation & Fidelity

The quality of safety planning has been shown to affect patient outcomes.^{61,62} Providers in both comparator groups will be trained on suicide screening and safety planning to minimize variation in these elements across intervention groups. The study will include a process evaluation to assess the consistency with which screening and safety planning interventions are completed, with process data collected and evaluated throughout the enrollment period using a dashboard.

The timing, type (phone vs text vs email), and number of attempted and successful contacts from the Hotline (“dose” and timing of follow-up contact) will be tracked and recorded by the Hotline for each study participant. Additionally, study staff will measure the fidelity of the follow-up interventions in several ways. For SPI+, Hotline follow-up specialists will be asked to follow a call template that includes essential elements of the intervention. Study staff will review these sheets routinely and will listen to a subset of calls to validate that the templates have been accurately completed. For SP+CC, study staff will review the text chat routinely to ensure that the tone and timing of text responses is aligned with the Caring Contacts model.

11. Discontinuation and Participant Withdrawal

11.1 Discontinuation of Study Intervention / Experimental Manipulation

Participants may choose to discontinue the follow-up intervention by contacting study staff. When a participant discontinues the intervention but remains in the study, remaining study procedures will be completed as indicated in the study protocol.

Data to be collected at the time of study intervention discontinuation will include the following:

- The date of discontinuation of the intervention
- The reason(s) for discontinuing the intervention (if available)

The participant will be eligible to complete follow-up surveys, even if they are not participating in the assigned intervention.

11.2 Participant Discontinuation and Withdrawal from the Study

Participants are free to withdraw from participation in the study at any time upon written request to the SPARC Trial email account ([contact]). Additionally, study investigators may discontinue a participant from the study for the following reasons:

1. Lost to follow-up; unable to contact subject (see section 12.3 *Lost to Follow-Up*).

2. Any event or medical condition or situation occurs such that continued collection of follow-up study data would not be in the best interest of the participant.
3. Any event or situation occurs in which the safety or wellbeing of study staff is compromised by allowing a participant to continue to participate in the research, or at the PI's discretion.
4. The participant meets an exclusion criterion or fails to meet an inclusion criterion (either newly developed or not previously recognized) that precludes further study participation.

The date of discontinuation and reason for discontinuation or withdrawal from the study will be recorded in the SPARC Trial study records.

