5.3 Masking

This trial will be single masked, with most members of the study team including the lead biostatistician masked to the comparator group (treatment condition) randomly assigned to each participant. Due to the nature of the intervention, masking providers or study participants to the comparator received is not feasible. The PI and research coordination team will conduct study enrollment and fidelity monitoring activities that may reveal the treatment assignment of individual participants.

6. Study Population

The primary study population for this research is adult and adolescent patients in Emergency Departments and primary care settings in the St. Luke's Health System who are identified as being at risk for suicide and have a completed Safety Plan or Connection & Support Plan.¹

This study will recruit 1,382 participants (790 adults and 592 adolescents) from 32 clinical sites:

9 EDs and 23 primary care clinics.

The secondary study population for this research consists of providers and clinical staff at study sites. This population will be recruited to participate through email invitation. Employee email addresses will be obtained, for example, through the use of site champions/liaisons or Digital and Analytics analysts. Although there is no estimated sample size for this population, sufficient participation is anticipated to complete Aim 2 of this protocol.

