6.4 Populations for Analyses

Analyses will be completed using the following populations:

1. **Intention to Treat (ITT) Analytic Population:** Data for all participants that complete study enrollment will be included in this dataset.
2. **Safety Analysis Population:** The dataset shared with the Data & Safety Monitoring Board for safety analysis will include data for all participants who completed study enrollment (e.g., the ITT Analytic Population Dataset).
3. **Per-Protocol Analysis Population:** Data for a subset of participants who were retained for the duration of the study and completed the minimum assigned intervention (e.g. received at least one phone call (SPI+), or were sent at least 4 caring contacts (SP+CC)).
4. **Additional Populations:** Additional datasets may be developed to complete sensitivity analyses, for example, where missing data have been imputed using different techniques.

7. Study Procedures

Pre-Consent – All participants (All activities are standard of care)

- C-SSRS screening for suicide risk at clinic or ED visit
- Development of safety plan or a connection and support plan

Baseline / Enrollment Visit – All participants (During/following clinic or ED visit)

- Study enrollment and informed consent
- Baseline Survey
 - Baseline survey includes questions related to demographics, socioeconomic status, gender identity, sexuality, religion, drug and alcohol use, quality of life, loneliness, self-harm and suicidal behavior.

Follow-Up Intervention – SPI+ participants

- Follow-up phone calls from the Hotline
 - 1 call within 72 hours of study enrollment to connect with the participant.
 - Series of 1-6 phone calls, based on participant's preference.
 - See *Description of Interventions*.

Follow-Up Intervention – SP+CC participants

- Follow-up phone call and caring text or email messages from the Hotline
 - 1 call within 72 hours of study enrollment to connect with the participant.
 - 25 personalized caring text or email messages sent according to a standardized schedule over a 12-month period.
 - See *Description of Interventions*.

2-Week Patient Satisfaction Survey – All participants (REDCap survey link sent via text or email)

- Patient satisfaction survey related to intervention received

6 Month Outcome Assessment – All participants (+ 4 weeks variance window) (REDCap survey link sent via email or text, or phone call)

- 6-Month Outcomes Survey

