11.3 Lost to Follow-Up

A study participant will be considered lost to follow-up if s/he fails to complete both study follow-up assessments and study staff are unable to contact the participant after at least 3 attempts. The following actions must be taken before a participant will be declared lost to follow-up.

- Study staff will attempt to contact the participant, re-send the REDCap survey or reschedule the missed phone-based assessment, and ascertain whether the participant wishes to and/or should continue in the study
- The study staff will make every effort to regain contact with the participant (using text, email, phone call, and/or alternative means of contact).
- Should the participant continue to be unreachable, s/he will be considered lost to follow-up and will be withdrawn from the study.

12. Data & Safety Monitoring

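### Section 11.2 lets investigators who may know the arm remove randomised participants from the study for ineligibility that arises after randomisation, which can create outcome-related missing data

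*Protocol*

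**What the plan says.** Protocol section 11.2 states that "study investigators may discontinue a participant from the study for the following reasons" and lists four. The fourth covers a participant who meets an exclusion criterion or "fails to meet an inclusion criterion (either newly developed or not previously recognized) that precludes further study participation". The third, about staff safety, ends with an open clause: "by allowing a participant to continue to participate in the research, or at the PI's discretion". The second applies where "continued collection of follow-up study data would not be in the best interest of the participant", so the section treats discontinuation from the study as the end of follow-up data.

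Section 11.1 deals with a different state, in which a participant stops the intervention but stays in the study. There, "The participant will be eligible to complete follow-up surveys, even if they are not participating in the assigned intervention". Section 11.2 has no matching provision for someone an investigator removes.

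Section 11.3 says of a participant who cannot be reached that "s/he will be considered lost to follow-up and will be withdrawn from the study". This applies only after both follow-up assessments are missed and at least three contact attempts have failed.

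On knowledge of the arm, section 5.3 says: "The PI and research coordination team will conduct study enrollment and fidelity monitoring activities that may reveal the treatment assignment" of individual participants. On the analysis set, section 6.4 says of the ITT population: "Data for all participants that complete study enrollment will be included in this dataset". Section 14.3 plans multiple imputation if the data are missing at random, and checks sensitivity to the imputation approach and variables.

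**The concern.** Removing someone found later to have been ineligible at entry is one thing. Removing someone because eligibility has changed since randomisation is another, because the change happens after treatment has begun and may be part of how the participant is doing. In section 6.1.2 the criteria that can change are phone access throughout the study, the ability to use email, the ability to consent (acute psychosis and intoxication are given as examples of its absence) and a provider's judgement that participation is unsuitable. Several of these could accompany worsening suicidality, which is what the primary outcome measures.

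The people applying the rule are not reliably masked, and the arms generate different information. Section 12.4 makes this argument itself: it declines real-time adverse event tracking because unequal contact would lead to unequal ascertainment, and relies on the 6- and 12-month assessments to keep ascertainment equal. Newly developed ineligibility is also noticed in real time. Acting on it by ending follow-up reopens the problem that section 12.4 set out to avoid. At stake are the primary C-SSRS comparison and, for the same people, the survey-based secondary and safety outcomes.

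**Working it through.** The rule has no figure of its own to reproduce, so the check has two parts: reading the sections together, and an illustration of size.

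**Reading the sections together**

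1. *Does reason 4 end outcome collection?* It discontinues the person from the study. Section 11.1 preserves surveys only for those who remain in the study, and reason 2 of 11.2 speaks of stopping follow-up data. The natural reading is that surveys stop, although reason 4 does not say so outright.
2. *Can the reason relate to outcome?* Yes, for loss of ability to consent and provider judgement, and plausibly for phone access.
3. *Can it relate to arm?* SPI+ starts with a call that includes a risk assessment and offers further calls on a schedule running to day 90 (10.2). SP+CC has one call and then messages (10.4). Study staff review call templates, listen to some calls and read text chats (10.6). Changes could reach the study team more often from one arm than the other.
4. *Does the ITT set repair it?* No. Section 6.4 keeps the person in the dataset with the outcome blank.
5. *Does imputation repair it?* Only under missing at random. If a person is removed before 6 months and no one removed in this way has a later score, the data contain nothing from which to learn how removed people fared.

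**Illustration of size**

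Let q be the extra share of one arm removed under reason 4, and D the amount by which removed participants' C-SSRS scores exceed those of participants who stay. D is taken as equal in both arms, and other missingness as ignorable. The full-arm mean equals the retained mean plus (share removed × D), so the complete-case contrast shifts by

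bias = q × D.

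Neither q nor D is in the protocol; both are assumptions.

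| q (excess in one arm) | D = 1 | D = 2 | D = 3 |
|---|---|---|---|
| 2 points | 0.02 | 0.04 | 0.06 |
| 3 points | 0.03 | 0.06 | 0.09 |
| 5 points | 0.05 | 0.10 | 0.15 |
| 10 points | 0.10 | 0.20 | 0.30 |

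With 1:1 allocation (assumed; the ratio is not stated), 3 points is 0.03 × 395 ≈ 12 adults or 0.03 × 296 ≈ 9 adolescents. If q is zero and D is the same in both arms, the shift is zero.

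**Yardsticks**

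- The target difference in section 14.2 is 1 unit with SD 2. Against it, 0.06 to 0.09 is 6% to 9%.
- The difference detectable with the stated sample after 30% dropout, at two-sided alpha 0.05:
  - Adults: 790 × 0.70 = 553; (1.960 + 1.282) × 2 × √(4/553) ≈ 0.55 units at 90% power.
  - Adolescents: 592 × 0.70 = 414.4; (1.960 + 0.842) × 2 × √(4/414.4) ≈ 0.55 units at 80% power.
  - Against 0.55, 0.06 to 0.09 is 11% to 16%, and the largest table entry, 0.30, is about 55%.

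The two yardsticks differ because the stated 790 and 592 exceed what 1 unit, SD 2 and 30% dropout require (243 and 180 by the usual two-sample formula). That is a separate matter on which this point does not depend. It does mean that the loss of numbers is not the worry here; bias is.

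**The case against.** The strongest reply is that reason 4 is narrow and discretionary. It says that investigators may act, and only where the failure precludes further participation. Losing a phone need not qualify, since survey links can go by email. Psychosis and intoxication are examples of inability to consent, not exclusions in their own right. The rule has proper uses, such as an entry error found late. Unmasking is only a possibility, and most of the team, including the lead biostatistician, is masked. Reasons for withdrawal are recorded, the DSMB reviews retention at 6 and 12 months, and imputation is planned. Analyses for data missing not at random may be in a statistical analysis plan that is not shown.

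Much of this stands. It makes the bias possible rather than established, and its frequency unknown. It does not remove the point: the rule expressly reaches newly developed failures, recording a reason does not recover an outcome, and a later sensitivity analysis is weaker than collecting the score.

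Four stronger readings are tempting, and the protocol does not support them:

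- *That withdrawing lost participants creates missing C-SSRS data.* Section 11.3 applies only after both assessments have been missed, so the scores are already absent.
- *That death ascertainment is at risk.* Section 17.13 keeps National Death Index follow-up for the ITT population for up to ten years.
- *That 11.2 contradicts 11.1.* One covers leaving the study and the other leaving the intervention. The protection in 11.1 is simply not carried over.
- *That up to 30% would lose record-based outcomes.* The 30% in section 14.2 is a dropout allowance for sample size, and nothing says that record extraction stops on withdrawal.

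**Conclusion.** The point holds as a weakness in a stated rule. Reason 4 of section 11.2 permits people who may know the arm to end outcome collection for randomised participants on grounds that arise after randomisation and can be related to outcome. Neither ITT membership nor imputation under missing at random restores what is then not collected.

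A reader should not infer that the primary comparison is biased, only that it can be. The size is illustrative: 0.06 to 0.09 C-SSRS units under an assumed 3-point imbalance and a 2- to 3-unit gap, and 0.02 to 0.30 units over the other imbalances and gaps tried. All of these rest on an assumed difference between arms in removal rates. If it occurs, the arm that loses more of its worse-off participants will look better than it is.

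For record-based outcomes the finding is narrower. Sections 11.2 and 11.3 leave open whether EPIC, EDIE and claims data on ED return and outpatient uptake are still used after withdrawal. These sources need no survey response, so the ambiguity is worth closing. No change to the sample size follows.

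**What to change.** - **Section 11.2, reason 4:** state that ineligibility which develops after randomisation does not end outcome collection. The 6- and 12-month surveys continue to be offered, as section 11.1 already provides for those who stop the intervention, subject to the participant's consent and to the existing best-interest and staff-safety grounds.
- **Sections 11.2 and 11.3:** state that investigator withdrawal or loss to follow-up does not end EPIC, EDIE or claims ascertainment of ED return and outpatient uptake unless the participant revokes consent for it.
- **Consent and assent forms:** add matching wording that separates stopping surveys from revoking record access.
- **Housekeeping:** section 11.2 points to section 12.3 for loss to follow-up, but 12.3 is Safety Outcomes and the text is in 11.3.

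The cost is a few sentences, a consent revision with IRB approval, and a few more survey invitations to people who may not answer.
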